11.7.2.3. Handling of Missing Data for Statistical Analysis

Element	Reporting Detail
Imputation	
 • There will be no imputation in any statistical analysis

11.8. Appendix 8: Values of Potential Clinical Importance

11.8.1. Laboratory Values

Haematology				
Laboratory Parameter	Units	Category	Clinical Concern Range	
			Low Flag (< x)	High Flag (>x)
Hematocrit	Ratio of 1	Male		0.54
		Female		0.54
		Δ from BL	↓0.075	
Hemoglobin	g/L	Male		180
		Female		180
		Δ from BL	↓25	
Lymphocytes	x10 ⁹ / L		0.8	
Neutrophil Count	x10 ⁹ / L		1.5	
Platelet Count	x10 ⁹ / L		100	550
White Blood Cell Count (WBC)	x10 ⁹ / L		3	20

Clinical Chemistry				
Laboratory Parameter	Units	Category	Clinical Concern Range	
			Low Flag (< x)	High Flag (>x)
Albumin	mmol/L		30	
Calcium	mmol/L		2	2.75
Creatinine	mmol/L	Δ from BL		↑ 44.2
Glucose	mmol/L		3	9
Magnesium	mmol/L		0.5	1.23
Phosphorus	mmol/L		0.8	1.6
Potassium	mmol/L		3	5.5
Sodium	mmol/L		130	150
Total CO ₂	mmol/L		18	32

Liver Function				
Test Analyte	Units	Category	Clinical Concern Range	
ALT/SGPT	U/L	High	≥ 2x ULN	
AST/SGOT	U/L	High	≥ 2x ULN	
AlkPhos	U/L	High	≥ 2x ULN	
T Bilirubin	μmol/L	High	≥ 1.5xULN	
T. Bilirubin + ALT	μmol/L U/L	High	1.5xULN T. Bilirubin + ≥ 2x ULN ALT	

Please review the IDSL standards for the Urinalysis PCI criteria.

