If a vital sign threshold is exceeded which may result in discontinuation as defined above, the vital sign should immediately be repeated twice (i.e 3 measurements within approximately 5 minutes) and the median value will be used at that time point. If the median value exceeds the threshold, it will be considered confirmed that the value exceeded the potential discontinuation threshold and the subject must be discontinued.

Cardiac Troponin/ B-type Natriuretic Peptide (BNP):

If the local cardiac troponin (cTn) is >ULN or B-type Natriuretic Peptide (BNP) is >2x ULN for the assay, that subject will undergo repeat cTn or BNP testing and urgent evaluation if symptoms suggestive of cardiac ischemia or heart failure are present, and a transthoracic echocardiogram will be performed.

Asymptomatic volunteers: If the repeat value is within the normal range, the subject may continue in the study with close follow-up of symptoms. If the repeat value for cTn is >ULN or BNP is >2x ULN the subject must be discontinued from the study.

Symptomatic volunteers: Cardiology consultation will be obtained immediately for any subject with new signs or symptoms suggestive of cardiac ischemia or heart failure and the subject must be discontinued from the study. Concerning symptoms may include:

- chest pain,
- increased shortness of breath
- rapid or irregular heartbeat
- diaphoresis
- anxiety
- fatigue, tiredness
- confusion

Tympanic Temperature:

- Confirmed (median of 3 measurements) $\geq 38.5^{\circ}\text{C}$ at any time point between bolus/infusion initiation and 1 hour after completion of the dosing.

Respiratory Issues:

- In case the subject complains of dyspnea or shortness of breath, or if there is objective evidence of bronchospasm or other respiratory difficulty, the subject will be immediately evaluated and if confirmed the subject must be discontinued from the study.

Neuropsychiatric Issues:

Suicidal Ideation and Behaviour:

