10.3.5.3. Clinical Laboratory Evaluation

All haematology, urinalysis and clinical chemistry laboratory values will be flagged high or low relative to their reported normal ranges. Separate listings describing subjects with haematology and clinical chemistry laboratory values with values of potential clinical concern will be produced.

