11.5.2. Reporting Standards

Reporting Standards	
General	

 The current GSK Integrated Data Standards Library (IDSL) will be applied for reporting, unless otherwise stated: 
 4.03 to 4.23: General Principles 5.01 to 5.08: Principles Related to Data Listings 6.01 to 6.11: Principles Related to Summary Tables 7.01 to 7.13: Principles Related to Graphics 	
Formats	

 All data will be reported according to the actual treatment the participant received unless otherwise stated. GSK IDSL Statistical Principles (5.03 & 6.06.3) for decimal places (DP's) will be adopted for reporting of data based on the raw data collected. Numeric data will be reported at the precision collected on the eCRF. The reported precision from non eCRF sources will follow the IDSL statistical principles but may be adjusted to a clinically interpretable number of DP's. 	
Planned and Actual Time	

 Reporting for tables, figures and formal statistical analyses: 
 Planned time relative to dosing will be used in figures, summaries, statistical analyses and calculation of any derived parameters, unless otherwise stated. The impact of any major deviation from the planned assessment times and/or scheduled visit days on the analyses and interpretation of the results will be assessed as appropriate. Reporting for Data Listings: 
 Planned and actual time relative to study drug dosing will be shown in listings (Refer to IDSL Statistical Principle 5.05.1). Unscheduled or unplanned readings will be presented within the participant's listings. 	

Reporting Standards	

 Visits outside the protocol defined time-windows (i.e. recorded as protocol deviations) will be included in listings but omitted from figures, summaries and statistical analyses. 	
Unscheduled Visits	

 Unscheduled visits will not be included in summary tables. Unscheduled visits will not be included in figures. All unscheduled visits will be included in listings. 	
Descriptive Summary Statistics	
Continuous Data	Refer to IDSL Statistical Principle 6.06.1
Categorical Data	N, n, frequency, %
Reporting of Pharmacokinetic Concentration Data	
Descriptive Summary Statistics	Refer to IDSL Statistical Principle 6.06.1 Assign zero to NQ values (Refer to GUI_51487 for further details)

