11.10.10. ICH Listings

ICH: Listings					
No.	Population	IDS / Example Shell	Title	Programming Notes	Deliverable [Priority]
Subject Disposition					
1.	All Subjects	ES2	Listing of Reasons for Study Withdrawal	ICH E3	DR, SAC
2.	Screened Subjects	ES7	Listing of Reasons for Screen Failure	Journal Guidelines	SAC
3.	All Subjects	BL1	Listing of Subjects for Whom the Treatment Blind was Broken	ICH E3	DR, SAC
4.	All Subjects	TA1	Listing of Randomised and Actual Treatments	IDS	DR, SAC
Protocol Deviations					
5.	All Subjects	DV2	Listings of Important Protocol Deviations	ICH E3	DR, SAC
6.	All Subjects	IE3	Listing of Subjects with Inclusion/Exclusion Criteria Deviations	ICH E3	DR, SAC
Demographic and Baseline Characteristics					
7.	All Subjects	DM2	Listing of Demographic Characteristics	ICH E3	SAC
8.	All Subjects	DM9	Listing of Race	ICH E3	SAC
Populations Analysed					
9.	Screened	SP3	Listing of Participants Excluded from Any Population	ICH E3	SAC
Prior and Concomitant Medications					
10.	All Subjects	CP_CM3	Listing of Concomitant Medications	IDS	SAC

ICH: Listings					
No.	Population	IDSL / Example Shell	Title	Programming Notes	Deliverable [Priority]
Exposure and Treatment Compliance					
11.	All Subjects	EX3	Listing of Exposure Data	ICH E3	SAC
Adverse Events					
12.	All Subjects	AE8CP	Listing of All Adverse Events	ICH E3	DR, SAC
13.	All Subjects	AE2	Listing of Relationship Between Adverse Event System Organ Classes, Preferred Terms, and Verbatim Text	IDSL	SAC
14.	All Subjects	AE7	Listing of Subject Numbers for Individual Adverse Events	ICH E3	SAC
Serious and Other Significant Adverse Events					
15.	All Subjects	AE8CPa	Listing of Serious Adverse Events	ICH E3	DR, SAC
16.	All Subjects	AE8CPa	Listing of Fatal Serious Adverse Events	ICH E3	SAC
17.	All Subjects	AE8CP	Listing of Adverse Events Leading to Withdrawal from Study / Permanent Discontinuation of Study Treatment	ICH E3	DR, SAC
18.	All Subjects	AE14	Listing of Reasons for Considering as a Serious Adverse Event		SAC
19.	All Subjects	AE8CP	Listing of All Drug-Related Fatal Serious Adverse Events		SAC
All Laboratory					
20.	All Subjects	LB5	Listing of All Laboratory Data for Participants with Any Value of Potential Clinical Importance	ICH E3 Display ALL labs for a subject who experienced a value of potential clinical importance. Include time with date	SAC

ICH: Listings					
No.	Population	IDS / Example Shell	Title	Programming Notes	Deliverable [Priority]

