21.	All Subjects	LB5	Listing of Laboratory Values of Potential Clinical Importance	Include time with date	SAC
22.	All Subjects	LB14	Listing of Laboratory Data with Character Results	ICH E3 Dipstick results	SAC
23.	All Subjects	UR2A	Listing of Urinalysis Data for Participants with Any Value of Potential Clinical Importance	ICH E3 Display ALL data for a subject who experienced a value of potential clinical importance.	SAC
ECG					
24.	All Subjects	EG3	Listing of All ECG Values for Participants with Any Value of Potential Clinical Importance	IDS Display ALL ECGs for a subject who experienced a value of potential clinical importance.	SAC
25.	All Subjects	EG3	Listing of ECG Values of Potential Clinical Importance	IDS	SAC
26.	All Subjects	EG5	Listing of All ECG Findings for Participants with an Abnormal ECG Finding	IDS	SAC
27.	All Subjects	EG5	Listing of Abnormal ECG Findings	IDS	SAC
28.	All Subjects	EG3	Listing of All ECG Values		SAC
29.	All Subjects	EG3	Listing of All Change from Baseline ECG Values		SAC

ICH: Listings					
No.	Population	IDS / Example Shell	Title	Programming Notes	Deliverable [Priority]
Vital Signs					
30.	All Subjects	VS4	Listing of All Vital Signs Data for Participants with Any Value of Potential Clinical Importance	IDS Display ALL Vital Signs for a subject who experienced a value of potential clinical importance. Include participants flagged with change from baseline vital sign values of PCI	SAC
31.	All Subjects	VS4	Listing of Vital Signs of Potential Clinical Importance	IDS	SAC
32.	All Subjects	VS4	Listing of Change from Baseline in Vital Signs of Potential Clinical Importance	IDS	SAC
33.	All Subjects	VS4	Listing of All Vital Signs Values		SAC
34.	All Subjects	VS4	Listing of All Change from Baseline Vital Signs Values		SAC

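### SAP 11.8.1 sets no clinical-importance limit for cTnI or BNP, so a rise large enough to force a stop does not by itself reach Table 2.10 or Listings 20 and 21

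*SAP*

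**What the plan says.** **Protocol.** Table 15 (Appendix 2) places cTnI and BNP in the clinical chemistry panel. Under Section 8.1.4, a cTn above ULN or a BNP above 2x ULN leads to a repeat test and an echocardiogram. For asymptomatic volunteers the rule then reads: "If the repeat value for cTn is >ULN or BNP is >2x ULN the subject must be discontinued from the study". Section 10.3.5.3 adds two reporting statements: "All haematology, urinalysis and clinical chemistry laboratory values will be flagged high or low relative to their reported normal ranges" and "Separate listings describing subjects with haematology and clinical chemistry laboratory values with values of potential clinical concern will be produced".

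**SAP.** Section 11.8.1 gives PCI limits for haematology, clinical chemistry and liver function, and closes with "Please review the IDSL standards for the Urinalysis PCI criteria". It has no entry for cTnI or BNP. Two listings depend on those limits: Listing 20, "Listing of All Laboratory Data for Participants with Any Value of Potential Clinical Importance", and Listing 21, "Listing of Laboratory Values of Potential Clinical Importance". For results outside the schedule, Section 11.5.2 says "Unscheduled visits will not be included in summary tables" and "All unscheduled visits will be included in listings".

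**The concern.** The protocol's risk assessment names cTn and BNP monitoring and stopping criteria as mitigation for the cardiac findings in rats. Both markers are also in the minimum data set for dose-escalation review (Appendix 3). Safety is the primary objective. According to the SAP introduction, the study ended because a link between the drug and a ventricular tachycardia could not be ruled out.

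A reader of the report would expect to find each subject's cTnI and BNP course, including any repeat that decided a discontinuation. If the PCI table is applied as written, nothing planned guarantees that. A stopped subject could be identified without the report showing the marker values, how far they stood above the limit, whether the repeat confirmed the first result, or how other subjects compared.

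**Working it through.** The point involves no sample size, power or error rate. The check is to trace where a cTnI or BNP value would go under the SAP's own rules.

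**1. Are the markers in the PCI table?** SAP 11.8.1 lists:
- six haematology analytes;
- nine chemistry analytes: albumin, calcium, creatinine, glucose, magnesium, phosphorus, potassium, sodium and total CO2;
- four liver tests (ALT, AST, alkaline phosphatase, total bilirubin) and one bilirubin-plus-ALT combination.

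Entries for cTnI or BNP: 0. The only mention of either marker in the SAP is exclusion criterion 6 in Appendix 1. Magnesium, phosphorus and total CO2 have limits although protocol Table 15 does not include them, so the PCI table was not matched to this protocol's panel.

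**2. How do other stopping measures compare?** Several have a SAP limit that is reached at or before the stopping limit:

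| Measure | Protocol stop | SAP PCI limit |
|---|---|---|
| ALT | >=3x ULN | >=2x ULN |
| QTc | >500 msec | >=500 msec (top category) |
| Systolic pressure | <=80 or >=180 mmHg | <85 or >160 mmHg |
| Heart rate | >=130 bpm | >110 bpm |
| cTn | >ULN | none |
| BNP | >2x ULN | none |

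**3. Which tables would hold a scheduled rise?**
- Table 2.10 (chemistry by PCI) would not count it, because there is no limit.
- Table 2.9 (change from baseline) and Table 2.11 (worst case against the normal range) should include it, if those tables carry every chemistry analyte in protocol Table 15.
- Table 2.11 classifies against the normal range only. A BNP just above ULN and a BNP above 2x ULN both count as High.

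**4. Which listings would show individual values?**
- Listing 20 shows all laboratory data for a subject, but only if that subject has at least one PCI value.
- Listing 21 shows PCI values only.
- Listing 22 covers dipstick results and Listing 23 covers urinalysis.
- Listings 36 and 37 cover echocardiogram and telemetry findings.
- No listing among Listings 1 to 41 is dedicated to cTnI or BNP.
- ECG and vital signs, by contrast, have all-subject listings (28 and 33).

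**5. Where does the confirming repeat go?** The SAP allows two readings:
- As an unscheduled result, it is kept out of summary tables (11.5.2). It is meant for listings, but only Listing 20 could hold it, and only if another analyte triggers that listing.
- As a further measurement at one time point, 11.6.1 would average it with the first value, or keep the value closest to the target.

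On either reading, no table shows the initial and repeat results as a pair.

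**6. How long would a dedicated listing be?** The current schedule for Part A has six sample times: screening, Day -1, Day 1 (6 h), and Days 2, 4 and 8. Assume 16 subjects in Cohorts 1 and 2, and 2 sentinels in Cohort 3.
- If Cohorts 1 and 2, planned for discharge on Day 4 (protocol Table 4), had five sample times: 16 x 5 + 2 x 6 = 92 sample times, x 2 analytes = 184 results.
- If they had six: 18 x 6 = 108 sample times, x 2 = 216 results.

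Repeats would be extra. The sampling schedule actually used in Cohorts 1 and 2 is not in the current documents, which is why this is a range.

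**The case against.** **Other standards may supply a limit.** SAP 7.2 bases laboratory evaluations on GSK Core Data Standards, SAP 11.5.2 applies the IDSL unless otherwise stated, and the display specifications are available only on request. None of these can be inspected here. This objection stands as a limit on confidence. SAP 11.8.1 itself points to the IDSL only for urinalysis, which suggests the rest of its table is meant to be complete, but it does not prove it.

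**The tables already show a good deal.** Protocol 10.3.4 makes minimum and maximum part of the default summaries, so Table 2.9 should show the largest change per dose group. Cohort 3 stopped after sentinel dosing with one active subject, so the 1.3 mg column would be that subject's own course. Entry required both markers to be no higher than ULN, so a post-dose High in Table 2.11 would normally be new. All of this stands for scheduled values. It does not supply the ratio to ULN, the BNP 2x cut or the repeat result.

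**A reader might infer that the protocol's listing commitment is broken.** The text does not clearly support that. Section 10.3.5.3 promises listings of values of potential clinical concern but sets no limits and names neither marker. Other Table 15 tests, such as BUN and total protein, have no limit either. Nothing in the documents requires PCI limits to match stopping rules.

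**A reader might also infer that these are the only stopping measures without a display.** That does not hold. Tympanic temperature has a stopping limit of 38.5 C and no PCI limit. Protocol 10.3.5.4 names only blood pressure and heart rate as the vital signs data to be listed, so temperature may be in the same position.

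**Nor do the documents say that either marker rose in any subject.** The ventricular tachycardia has its own reporting routes through the adverse event, ECG and telemetry listings. A subject stopped for a marker rise would appear in Listing 1, and probably in Listings 12, 17 and 36, though none of these is set up to display marker values.

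**Conclusion.** The point holds as a low-severity reporting gap, with moderate confidence. By the SAP's stated limits, a cTnI or BNP value that compels discontinuation is not flagged as clinically important (0 of 9 chemistry limits). It does not by itself enter Table 2.10 or Listings 20 and 21. No table separates BNP above 2x ULN from BNP above ULN, and no planned listing shows individual values or the initial and repeat pair unless another analyte happens to be flagged.

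This rests on two assumptions: that no unseen GSK standard adds a limit, and that Tables 2.9 and 2.11 include both markers. If the second fails, the gap is wider, because scheduled rises would not appear even in aggregate.

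It would be wrong to infer that participants were less protected. Monitoring, individual stopping and dose-escalation review run on protocol rules that do not depend on the SAP's PCI table.

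**What to change.** 1. Add cTnI above ULN and BNP above 2x ULN to SAP 11.8.1, taken from protocol 8.1.4, so that both feed Table 2.10 and Listings 20 and 21.
2. Add one all-subject listing of cTnI and BNP beside Listings 36 and 37. It should show scheduled, repeat and unscheduled results, with dose, actual time from dose and ULN, and mark which results are repeats.

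The cost is two limits and one short listing of data already collected, with no new sample, visit or procedure. Some isolated rises unrelated to the drug will be listed, and the cTnI limit partly duplicates the High category in Table 2.11. The BNP cut-off and the individual listing are the new information. If a GSK standard already sets these limits, citing it in SAP 11.8.1 would replace step 1 only.

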11.8.2. ECG

ECG Parameter	Units	Clinical Concern Range	
		Lower	Upper
Absolute			
Absolute QTc Interval	msec	> 450 [1]	
		> 450 [2]	≤ 479 [2]
		≥ 480 [2]	≤ 499 [2]
		≥ 500 [2]	
Absolute PR Interval	msec	< 110 [1]	> 220 [1]
Absolute QRS Interval	msec	< 75 [1]	> 110 [1]
Change from Baseline			
Increase from Baseline QTc	msec	> 60 [1]	
	msec	> 30 [2]	≤ 59 [2]
	msec	≥ 60 [2]	

NOTES:

1. To be used to flag ECG values of PCI for tables not split by category
2. To be used to flag ECG values of PCI for tables which are split by category

11.8.3. Vital Signs

Vital Sign Parameter (Absolute)	Units	Clinical Concern Range	
		Lower	Upper
Systolic Blood Pressure	mmHg	< 85	> 160
Diastolic Blood Pressure	mmHg	< 45	> 100
Heart Rate	bpm	< 40	> 110

Vital Sign Parameter (Change from Baseline)	Units	Clinical Concern Range			
		Decrease		Increase	
		Lower	Upper	Lower	Upper
Systolic Blood Pressure	mmHg	≥ 20	≥ 40	≥ 20	≥ 40
Diastolic Blood Pressure	mmHg	≥ 10	≥ 20	≥ 10	≥ 20
Heart Rate	bpm	≥ 15	≥ 30	≥ 15	≥ 30

11.9. Appendix 9: Abbreviations & Trade Marks

11.9.1. Abbreviations

Abbreviation	Description
3-HAA (3-HAT)	3-hydroxyanthranilic acid
µg	Microgram
ADaM	Analysis Data Model
AE	Adverse Event
AIC	Akaike's Information Criteria
A&R	Analysis and Reporting
AUC	AUC Area under concentration-time curve
AUC(0-inf)	Area under the concentration-time curve from time zero (pre-dose) extrapolated to infinite time
AUC(0-t)	Area under the concentration-time curve from time zero (pre-dose) to last time of quantifiable concentration within a participant across all treatments
AUC(0-tau)	Area under the concentration-time curve from time zero (pre-dose) during a dosage interval
AUC (Ro)	Observed Accumulation Ratio for AUC observed accumulation ratio for AUC
CDISC	Clinical Data Interchange Standards Consortium
CI	Confidence Interval
CL	Clearance
Cmax	Maximum observed concentration
CPMS	Clinical Pharmacology Modelling & Simulation
CS	Clinical Statistics
CSR	Clinical Study Report
C-SSRS	Columbia Suicide Severity Rating Scale
(C _T)	Trough concentration (C _T)
CTR	Clinical Trial Register
CV _b / CV _w	Coefficient of Variation (Between) / Coefficient of Variation (Within)
DBF	Database Freeze
DBR	Database Release
DOB	Date of Birth
DP	Decimal Places
eCRF	Electronic Case Record Form
EMA	European Medicines Agency
FDA	Food and Drug Administration
FDAAA	Food and Drug Administration Clinical Results Disclosure Requirements
GSB	Global Safety Board
GSK	GlaxoSmithKline
IA	Interim Analysis
ICH	International Conference on Harmonization
IDMC	Independent Data Monitoring Committee
IDS	Integrated Data Standards Library
IMMS	International Modules Management System
IP	Investigational Product

Abbreviation	Description
ITT	Intent-To-Treat
KYNA	kynurenic acid
MMRM	Mixed Model Repeated Measures
PCI	Potential Clinical Importance
PD	Pharmacodynamic
PDMP	Protocol Deviation Management Plan
PK	Pharmacokinetic
PKCNC	Pharmacokinetic concentration
PP	PK Parameter
PopPK	Population PK
QA	quinolinic acid
QC	Quality Control
QTcF	Frederica's QT Interval Corrected for Heart Rate
QTcB	Bazett's QT Interval Corrected for Heart Rate
RAP	Reporting & Analysis Plan
RAMOS	Randomization & Medication Ordering System
SAC	Statistical Analysis Complete
SDSP	Study Data Standardization Plan
SDTM	Study Data Tabulation Model
SOP	Standard Operation Procedure
TA	Therapeutic Area
TFL	Tables, Figures & Listings
TRP	Tryptophan
XA	xanthurenic acid

11.9.2. Trademarks

Trademarks of the GlaxoSmithKline Group of Companies	Trademarks not owned by the GlaxoSmithKline Group of Companies
NONE	NONMEM SAS WinNonlin

11.10. Appendix 10: List of Data Displays

11.10.1. Data Display Numbering

The following numbering will be applied for RAP generated displays:

Section	Tables	Figures
Study Population	1.1 to 1.11	N/A
Safety	2.1 to 2.28	N/A
Pharmacokinetic	3.1 to 3.3	3.1
Pharmacodynamic	4.1 to 4.2	4.1 to 4.4
Section	Listings	
ICH Listings	1 to 34	
Other Listings	35 to 41	

11.10.2. Mock Example Shell Referencing

Non IDSL specifications will be referenced as indicated and if required example mock-up displays provided in [Appendix 11: Example Mock Shells for Data Displays](#)

Section	Figure	Table	Listing
Study Population	POP_Fn	POP_Tn	POP_Ln
Safety	SAFE_Fn	SAFE_Tn	SAFE_Ln
Pharmacokinetic	PK_Fn	PK_Tn	PK_Ln
Pharmacodynamic	PD_Fn	PD_Tn	PD_Ln

NOTES:

- Non-Standard displays are indicated in the 'IDSL / Example Shell' or 'Programming Notes' column as '[Non-Standard] + Reference.'

11.10.3. Deliverables

Delivery	Description
DR	Dry Run
SAC	Statistical Analysis Complete

11.10.4. Study Population Tables

Study Population Tables					
No.	Population	IDSL / Example Shell	Title	Programming Notes	Deliverable [Priority]
Subject Disposition					
1.1.	All Subjects	ES8	Summary of Subject Status and Reason for Study Withdrawal (Part A)	ICH E3, FDAAA, EudraCT	DR, SAC
1.2.	Screened	ES6	Summary of Screening Status and Reasons for Screen Failure (Part A)	Journal Requirements	DR, SAC
Demographic and Baseline Characteristics					
1.3.	All Subjects	DM1	Summary of Demographic Characteristics (Part A)	ICH E3, FDAAA, EudraCT	DR, SAC
1.4.	Enrolled	DM11	Summary of Age Ranges (Part A)	EudraCT	DR, SAC
1.5.	All Subjects	DM5	Summary of Race and Racial Combinations (Part A)	ICH E3, FDA, FDAAA, EudraCT	DR, SAC
Protocol Deviations					
1.6.	All Subjects	DV1	Summary of Important Protocol Deviations (Part A)	ICH E3	DR, SAC
Populations Analysed					
1.7.	Screened	SP1	Summary of Study Populations (Part A)	IDSL	DR, SAC
Prior and Concomitant Medications					
1.8.	All Subjects	MH1	Summary of Current Medical Conditions (Part A)	ICH E3	SAC
1.9.	All Subjects	MH1	Summary of Past Medical Conditions (Part A)	ICH E3	SAC
1.10.	All Subjects	CM1	Summary of Concomitant Medications (Part A)	ICH E3	SAC
Exposure and Treatment Compliance					
1.11.	All Subjects	EX5	Summary of Exposure to Study Treatment (Part A)	ICH E3	DR, SAC

